2.2 STUDY OBJECTIVES

Primary objectives:

1. Explore baseline characteristics and drug utilization patterns of 11 commonly used antidepressant therapy during 90 days of acute treatment phase
 - Top 11 commonly used antidepressants according to local market data are as follows:
 - Escitalopram, paroxetine, fluoxetine, mirtazapine, duloxetine, sertraline, venlafaxine, tianeptine, vortioxetine, desvenlafaxine, bupropion
 - Proportion of antidepressants prescribed by sex, age (<20, 21-64, > 65), sex and age combined
 - Initial doses used, average daily doses of each antidepressants
 - Average length of treatment with index medication before therapy change occurs (switching, combination, augmentation, discontinuation)
 - Adherence and persistence measured by medication possession ratio during first 90 days of treatment period
2. Explore drug utilization patterns such as therapy changes, medication compliance and recurrence relationship, and risk of adverse outcomes during maintenance phase
 - The choice of antidepressant, average length of new treatment maintenance, average number of co-administered medications (e.g., atypical antipsychotics, mood stabilizer, thyroid hormone, psychostimulant) when following changes occur from initial monotherapy:
 - Switching
 - Combination
 - Augmentation
 - Medication compliance and recurrence
 - Compliance measured as adherence and persistence
 - Recurrence
 - Relationship between recurrence and compliance

PFIZER CONFIDENTIAL

- *Risk of adverse outcomes measurement between individual ADs that are well known to be treatment-related (e.g., hyponatremia, GI bleeding, fractures, falls, risk of intracranial hemorrhage, attempted suicide/self-harm, myocardial infarction, epilepsy/seizures, stroke/transient ischemic stroke)*

Secondary objectives:

1. *Choice of antidepressants and drug utilization patterns in patients with various comorbidities*
 - *Psychiatric comorbidities*
 - *Mild cognitive impairment (MCI)*
2. *The relationship of non-pharmacologic treatment and discontinuation, medication compliance*
 - *Non-pharmacologic treatments may include: cognitive behavioral therapy (CBT), frequency of physician visit during acute and maintenance phase of treatment*
 - *Frequency of visit during the first 3 months of acute phase and its relationship to treatment maintenance at 4, 5, 6, 7, 8, 9 month time points and discontinuation rate*
3. *Choice of antidepressants by non-psychiatric specialty*

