5.1 EFFICACY/EFFECTIVENESS ENDPOINT(S)

Medication compliance (persistence, discontinuation, adherence) along with recurrence are main primary efficacy endpoints and they are defined as follows:

1. MPR (medication possession ratio)
For each of 11 study drugs, the MPR will be calculated by (Days of medication possession from the prescriptions filled in the 180 days) / (180 days + extra days of drug supply from the last prescription fill during the 180 days)
2. Persistence
For each of 11 study drugs, the average length of treatment on the index drug during the first 180 day period (allowing 14 day permissible gap) will be

PFIZER CONFIDENTIAL

calculated. Switching, combination, augmentation, discontinuation will terminate the persistent period.

3. Discontinuation

For each of 11 study drugs chosen as index drug, the percentage of discontinuation in the first 90 days from the index date (acute treatment phase) will be measured (allowing 14 day permissible gap)

4. Adherence

For each of 11 study drugs chosen as index drug, adherence will be measured by MPR and persistence during the first 90 day and 180 day from the index date, respectively (acute treatment phase). MPR ≥ 0.75 and persistence ≥ 90 will be considered as adherence.

* For those period with any identified adverse outcome such as GI bleeding will be considered as a non-adherent period.

5. Recurrence

Recurrence during the acute treatment phase was operationally defined as either one of the following being satisfied:

- 1) Inpatient episode with a diagnosis code in Table 1
- 2) Inpatient episodes via the department of psychiatry or emergency medicine
- 3) Inpatient episode via nursing hospital
- 4) Emergency room visit with a diagnosis code in Table 1
- 5) Suicide attempt identified by the following KCD-7 codes:
 - T40 Poisoning by narcotics and psychodysleptics [hallucinogens]
 - T41 Poisoning by anaesthetics and therapeutic gases
 - T42 Poisoning by antiepileptic, sedative-hypnotic and antiparkinsonism drugs
 - T43 Poisoning by psychotropic drugs, not elsewhere classified
 - T54 Toxic effect of corrosive substances
 - T60 Toxic effect of pesticides
 - X60-X84 intentional self harm
- 6) Augmentation of the following non-AD drugs
 - Antipsychotic: amisulpride, aripiprazole, olanzapine, quetiapine, risperidone, perphenazine
 - Anticonvulsant: carbamazepine, valproic acid, lamotrigine
 - Mood stabilizer: lithium
 - Anxiolytic: buspirone
 - Thyroid hormone: levothyroxine, liothyronine

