5.2 SAFETY ENDPOINTS

Adverse outcomes are primary endpoints in this study and they include the following categories defined by KCD-7 diagnosis codes and/or NHI procedure codes appearing in medical claims data after the index date.

- GI bleeding
I850, I983, K2211, K226, K228, K250, K252, K254, K256, K260, K262, K264, K266, K270, K272, K274, K276, K280, K282, K284, K286, K290, K3181, K5521, K625, K920, K921, K922
- Fractures
S02, S12, S22, S32, S42, S52, S62, S72, S82, S92, T02, T08, T10, T12, T14.2
- Falls
W00-W19
- Intracranial hemorrhage
I60, I61, I62, I690, I691, I692, S064, S065, S066, S068
- Suicide attempt, self-harm
T40 Poisoning by narcotics and psychodysleptics [hallucinogens]
T41 Poisoning by anaesthetics and therapeutic gases
T42 Poisoning by antiepileptic, sedative-hypnotic and antiparkinsonism drugs
T43 Poisoning by psychotropic drugs, not elsewhere classified
T54 Toxic effect of corrosive substances
T60 Toxic effect of pesticides
X60-X84 intentional self-harm
- Myocardial infarction
I21.9, I21.4, I21.0, I21.1, I21.2, I21.3, I22.0A, I22.0B, I22.0C, I22.8A, I22.8B, I22.8C, I22.8D, I22.8E, I22.8F, I22.8G, I22.8H, I22.8I, I22.8, I22.9, I22.1A, I22.1B, I22.1C
- Epilepsy/seizures
G40.XX
- Stroke
 - Transient ischemic attack
G459, I63, I693
 - Hemorrhagic stroke
I60, I61, I62, I690, I691, I692
 - Ischemic stroke
I63

[NOTE] Hospitalization and CT or MRI codes such as brain CT or MRI procedure code for ischemic stroke and hemorrhagic stroke, or any CT or MRI for systemic embolism are also required for identification.

- Brain CT
HA441, HA451, HA461, HA471, HA851
- Brain MRI
HE101, HE102, HE135, HE201, HE202, HE235, HE301, HE302, HE401, HE402, HE501, HE502, HE535
- Any CT or MRI or CT

HA401-HA416, HA424, HA425, HA434, HA435, HA443-HA449, HA453, HA456-HA459, HA463-HA469, HA473-HA479, HA496, HA497, HA801, HA805, HA809, HA813, HA834, HA835, HA853, HA856, HA857-HA859, S852

- MRI
HE103-HE142, HE203-HE234, HE236-HE241, HE303-HE334, HE403-HE434, HE430-HE434, HE503-HE534, HE536-HE541, HF101, HF102, HF104-HF107, HF201, HF202, HF305, HF306
- Hyponatremia
Will be identified by prescription codes for vasopressin receptor antagonists such as tolvaptan (drug code=616501ATB)

CC
I

[figure not shown]

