7.2.2 Study Drug Analysis in Maintenance Phase

- To understand the top 11 antidepressants usage among the Korean patients with depression in maintenance treatment phase
- Primary analysis
- Endpoints:
 - Choice of study drug
 - Average length of new treatment maintenance
 - Average number of co-medications (e.g., atypical antipsychotics, mood stabilizer, thyroid hormone, psychostimulant) when following changes occur from initial monotherapy: switching, combination, augmentation
 - Medication compliance (adherence, discontinuation, and persistence)
 - Recurrence by each antidepressant, by compliance
 - Risk of adverse events
- Population: patients from the acute treatment phase who started maintenance treatment (after 90 days from the index date)
- Significance on continuous variables will be tested by ANOVA (if equal variance condition satisfied) or Kruskal-Wallis H test (otherwise). Provider specialty and other patient characteristics will be used to fit antidepressant choice by multivariate logistic regression analysis of each study drug choice.
- Covariates: antidepressant class covariates such as SSRIs, SNRIs, and other ADs will be used as grouping variables.
- Missing values will be dropped from the analysis
- The role of this analysis is to provide information on study antidepressants in the maintenance phase of drug therapy for Korean patients with depression.

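### Recurrence counts admissions via emergency medicine or a nursing hospital with no depression code, so non-depression admissions, including the study's own safety outcomes, can count as depression recurrence

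*SAP*

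**What the plan says.** SAP 5.1 names recurrence, with medication compliance, as a main primary efficacy endpoint. Item 5 counts a recurrence if any one criterion is met. Two criteria require a depression code: "1) Inpatient episode with a diagnosis code in Table 1" and "4) Emergency room visit with a diagnosis code in Table 1". Two do not: "2) Inpatient episodes via the department of psychiatry or emergency medicine" and "3) Inpatient episode via nursing hospital". SAP Table 3 repeats the list, and the post-acute definition reuses criteria 1 to 6 and adds a seventh. The recurrence entry in protocol Table 3 (section 9.3) had only the coded inpatient, coded emergency-room and suicide-attempt criteria. SAP section 1 logs the widening as made during data analysis.

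Three other statements bear on it:

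- SAP 5.2: "Adverse outcomes are primary endpoints in this study". They include GI bleeding, fractures, infarction and stroke. Ischemic and hemorrhagic stroke need a hospitalization to be identified.
- SAP 5.1 item 4: "For those period with any identified adverse outcome such as GI bleeding will be considered as a non-adherent period".
- SAP 2.2, primary objective 2, lists "Relationship between recurrence and compliance", and SAP 7.2.2 plans "Recurrence by each antidepressant, by compliance".

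**The concern.** A patient admitted through the emergency department with a fracture or a GI bleed meets criterion 2 whatever the state of the depression. That admission is then both a safety outcome and a depression recurrence.

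Two consequences follow for the drug comparison. Admissions unrelated to depression pull true differences towards the null. A drug with more adverse events can also gain recurrences for reasons unrelated to depression.

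A third concerns compliance. Because an adverse-outcome period is treated as non-adherent, the same event can push a patient towards non-adherence and towards recurrence. Matching or weighting on baseline characteristics does not remove a link created by the outcome definitions.

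**Working it through.** **Reading the criteria.** Suppose criteria 2 and 3 silently required a Table 1 code in any position. Both would then be subsets of criterion 1 and add nothing. They have effect only by adding admissions with no Table 1 code or, if criterion 1 is run on principal diagnosis, also admissions with depression as a secondary code. *Via* is undefined. Read as billing department it catches fewer admissions than read as route of entry, but neither reading imposes a diagnosis.

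**Inputs.** The documents give no admission rate, recurrence rate or recurrence window, so there is no plan figure to reproduce. Assumed:

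- e = 0.01 to 0.06 per year, non-depression admissions by these routes
- r = 0.30 to 0.50, recurrence risk from the other criteria
- f = 0.10 to 0.30, share of these admissions that are for 5.2-type events
- T = 90 days (length of the 91-180 day maintenance window for drug-use patterns in SAP Table 3), 180 days, and 550 days (30 June 2019 to 31 December 2020, an upper assumption)

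**Formulas.** x = 1 − exp(−eT/365). Observed risk = 1 − (1 − r)(1 − x). False share = (observed − r)/observed. For dilution, one drug has 0.7r. For the spurious ratio, e is replaced by e(1 + 0.5f) in one drug, that is, 1.5 times the rate of 5.2-type events only.

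Example with e = 0.06, r = 0.30, T = 180: x = 0.0292; observed = 1 − 0.70 × 0.9708 = 0.3204; false share = 0.0204/0.3204 = 6.4%; diluted ratio = (1 − 0.79 × 0.9708)/0.3204 = 0.727.

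| T (days) | False share | True 0.70 becomes at most | Largest spurious ratio, r = 0.30 | r = 0.50 |
|---|---|---|---|---|
| 90 | 0.2-3.3% | 0.71 | 1.005 | 1.002 |
| 180 | 0.5-6.4% | 0.73 | 1.009 | 1.004 |
| 550 | 1.5-17% | 0.77 | 1.024 | 1.011 |

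**Significance threshold.** The earlier HIRA study in protocol 9.5 found 752,190 new users in five years. The SAP intake is 1.5 years: 752,190 × 1.5/5 ÷ 11 = about 20,500 per drug, on an equal split and before the age cap. I take n = 20,000. The ratio reaching p<0.05 is exp(1.96 × √(2(1 − r)/(rn))) = 1.030 at r = 0.30 and 1.020 at r = 0.50. Using the inflated observed risk (e = 0.06, 550 days) gives 1.026 and 1.018. Every spurious ratio in the table is below its threshold.

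Applying 1.5 to all such admissions gives up to 1.031 at 180 days and 1.078 at 550 days. That needs a 5.2-event ratio of 1 + 0.5/f, which is 2.7 to 6.0.

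**If recurrence is rarer.** With r = 3-10% and an uncoded-admission risk of 0.5-3% over the window, also assumed, the false share is 4-49% and a true ratio of 0.80 becomes 0.81-0.90.

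**Compliance, 180 days, no true link.** Let a = 0.30-0.50 be the adherent share (protocol section 7 says below 50%), y = 1 − exp(−efT/365), and k the fraction of adherent patients with a 5.2-type admission who become non-adherent. Let t be the observed risk above, and b the same risk with 5.2-type admissions left out.

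- Risk if non-adherent = [(1 − a)t + ayk]/[(1 − a) + ayk]
- Risk if adherent = [(1 − y)b + y(1 − k)]/(1 − yk)

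At the most unfavourable corner (e = 0.06, f = 0.30, r = 0.30, a = 0.50), y = 0.0088, t = 0.3204 and b = 0.3144. The ratio is 1.002 for k = 0.05, 1.004 for k = 0.10, 1.019 for k = 0.50 and 1.038 for k = 1.

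**The case against.** **A deliberate trade-off.** The change is logged with before and after text and a general rationale. Protocol 9.9 acknowledges that diagnoses are miscoded, so a route-based criterion may catch depression admissions coded otherwise. That stands as a reason to keep the wider definition in view. It does not justify leaving emergency and nursing-hospital admissions unrestricted in the primary definition.

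**The effects are small.** This largely stands. A reader might infer that the definition will make a drug with more adverse events look significantly less effective. The documents give no rates that would support this, and under the assumed inputs no scenario confined to 5.2-type events reaches significance. A shorter window, which SAP 7.2.2 may imply, shrinks the effect further.

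**Compliance.** A reader might also infer that the recurrence-compliance relationship is largely an artefact. The documents do not support that. The SAP makes the period non-adherent, not the patient; adherence then requires MPR of at least 0.75 and persistence of at least 90. A patient with full possession must lose more than 0.25 × 180 = 45 days (22.5 days if MPR is taken over 90 days) to fail the MPR part. An event in days 1-90 also falls under the acute-phase recurrence definition, not the post-acute one.

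**Exploratory purpose.** The objectives are worded as exploration and SAP section 3 states no hypotheses. But protocol 9.7 compares recurrence across the 11 drugs and applies p<0.05, so the endpoint's meaning still matters.

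The self-harm overlap between recurrence and safety is explicit and was already in the protocol; it is not part of this point.

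**Conclusion.** The definition is wrong as written and should be fixed. Run literally, it counts admissions for other illnesses, including the study's own primary safety outcomes, as depression recurrence. That much rests on the text alone.

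The size cannot be derived from the documents. Under the stated assumptions, dilution is slight over 90 or 180 days and moderate over 550; it would be larger if true recurrence is rarer than 30-50%. The spurious drug ratio is at most 1.005, 1.009 and 1.024 over the three windows, so a false significant difference is not shown; that comparison depends on the assumed 20,000 users per drug. The built-in compliance ratio is about 1.00-1.004 if 5-10% of affected adherent patients become non-adherent, and reaches 1.038 only if all do. The case for the change is therefore mainly that readers could not tell depression recurrence from emergency admission for something else.

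**What to change.** In SAP 5.1 item 5 and SAP Table 3:

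1. Remove the emergency-medicine part of criterion 2 and all of criterion 3 from the primary definition. Table 1-coded admissions stay under criterion 1 and self-harm under criterion 5. Psychiatry admissions may stay.
2. In the primary definition itself, do not count as recurrence an admission that is counted as a 5.2 outcome, other than suicide attempt/self-harm.
3. State the diagnosis position used for criterion 1. Any-position coding without step 2 would leave the overlap in place, because a fracture admission listing depression as a secondary code would still count twice.
4. Report the current wider definition, with *via* defined, as a labelled sensitivity analysis.
5. Tabulate the number of recurrences contributed by each criterion, by drug. This replaces the assumed ranges with observed counts.
6. Record the change as an amendment made during data analysis, decided without reference to by-drug recurrence results.

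The cost is SAP wording, a re-run on the HIRA server and its export review (protocol 9.6). There will be fewer events, some depression-related admissions coded otherwise will be missed, and it is one more late endpoint change. Keeping the wider definition as a sensitivity analysis limits these losses.

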Recurrence after the acute treatment phase was operationally defined as either one of the following being satisfied:

- 1) ~6) the same as above
- 7) AD prescription after 30 days of drug holiday

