Persistence	Primary outcome	HIRA Database	
For each of 11 study drugs, the average length of treatment on the index drug during the first 180 day period (allowing 14 day permissible gap) will be calculated
 
Switching, combination, augmentation, discontinuation will terminate the persistent period

Discontinuation	Primary outcome	HIRA Database	For each of 11 study drugs chosen as index drug, the percentage of discontinuation in the first 90 days from the index date (acute treatment phase) will be measured (allowing 14 day permissible gap)
Adherence	Primary outcome	HIRA Database	
For each of 11 study drugs chosen as index drug, adherence will be measured by MPR and persistence during the first 90 day and 180 day period from the index date, respectively (acute treatment phase). MPR ≥ 0.75 and persistence ≥ 90 will be considered as adherence.
 
* For those period with any identified adverse outcome such as GI bleeding will be considered as non-adherent period

Drug utilization pattern in acute phase	Secondary outcome	HIRA Database	
During the first 90 day period starting from the index date, the following types of drug utilization pattern is recorded
 
- monotherapy (kept on the index medication)- switching (switched to other antidepressant)- combination (adding other antidepressant)- augmentation (adding other non-AD drug such as antipsychotic)
Drug utilization pattern in maintenance phase	Secondary outcome	HIRA Database	
During the second 90 day period (91 ~ 180 days) starting from the index date, the following types of drug utilization pattern is recorded
 
- choice of antidepressant- monotherapy (kept on the same medication)- switching (switched to other antidepressant)- combination (adding other antidepressant)- augmentation (adding other non-AD drug such as antipsychotic)

PFIZER CONFIDENTIAL

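### Augmentation counts as recurrence and also ends persistence (and a restart after a holiday presupposes that it has ended), so the primary recurrence-by-compliance result is partly set by the definitions, in a direction the SAP leaves open

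*SAP*

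**What the plan says.** SAP section 5.1 defines both sides of the comparison.

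- **Persistence (item 2; also Table 3 in section 5.4):** "the average length of treatment on the index drug during the first 180 day period (allowing 14 day permissible gap) will be calculated". The rule that ends it is: "Switching, combination, augmentation, discontinuation will terminate the persistent period".
- **Adherence (item 4):** "MPR ≥ 0.75 and persistence ≥ 90 will be considered as adherence".
- **Recurrence (item 5):** the list for the acute phase includes "6) Augmentation of the following non-AD drugs", followed by named antipsychotics, anticonvulsants, lithium, buspirone and thyroid hormones. For the period after the acute phase the SAP carries the list over, "1) ~6) the same as above", and adds "7) AD prescription after 30 days of drug holiday".

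Table 3 describes the utilization category broadly: "augmentation (adding other non-AD drug such as antipsychotic". The drugs named in recurrence item 6 are therefore a subset of what counts as augmentation.

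Section 2.2 puts the link between recurrence and compliance under primary objective 2, with compliance measured by adherence and persistence. Section 7.2.2 is labelled a primary analysis and lists recurrence by antidepressant and by compliance among its endpoints. The protocol's recurrence definition (section 9.3, Table 3) has neither item 6 nor item 7. Section 1 of the SAP discloses that they came in with an amendment made while data analysis was under way.

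**The concern.** A single claim can place a patient in the less compliant group and also count as that patient's recurrence. A link between the two then appears even if taking the drug has no bearing on relapse. Because this relationship is part of a primary objective, a reader of the results could not separate a real association from one built in by the definitions.

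The visible text of section 7.2.2 does not say which compliance measure groups the recurrence result, where persistence is cut, over what window recurrence is counted, or that compliance must be fixed before recurrence is counted. Figure 1 is not visible in the text available.

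**Working it through.** The plan states no rate, event count or risk ratio for this analysis, so there is no figure to reproduce. The first two steps follow from the wording alone. Steps 3 to 6 use assumed rates and only illustrate.

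**1. Item 6 against persistence.** A patient on the index drug who receives a listed non-AD drug on day d (d ≤ 180) has persistence capped at d and a recurrence on d. If d is below 90, persistence is below 90, so the adherence flag fails and the same claim is an acute-phase recurrence.

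**2. Item 7 against persistence.** A 30-day holiday from antidepressants is a gap of more than 14 days in the index drug. For the restart to fall in days 91-180, persistence must already have ended. Taken with step 1, patients with persistence of 180 days have exactly 0 item 6 or 7 events in days 91-180.

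**3. Persistence below 180 against 180 days, events in days 91-180.** Let p be the risk of items 1-5 in the window (assumed unrelated to compliance) and d the share of the not-fully-persistent group with an item 6 or 7 event. With no true effect:

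risk ratio = [p + (1 − p)d] / p = 1 + d(1 − p)/p

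- p = 5%, d = 1%: 1 + 0.01 × 0.95/0.05 = 1.19
- p = 2%, d = 5%: 1 + 0.05 × 0.98/0.02 = 3.45
- p = 1%, d = 20%: 1 + 0.20 × 0.99/0.01 = 20.8

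The ratio always exceeds 1 when d > 0. The documents give neither p nor d.

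**4. Persistence below 90 against 90 or more, same window.** Both groups can now have item 6 or 7 events, with shares d1 (below 90) and d2 (90 or more):

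risk ratio = [p + (1 − p)d1] / [p + (1 − p)d2]

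Restarts raise d1. Patients who stopped early and stayed off antidepressants cannot be augmented, which lowers d1. With p = 2%:

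- d1 = 5%, d2 = 10%: 0.069/0.118 = 0.58
- d1 = 10%, d2 = 5%: 0.118/0.069 = 1.71

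The direction is open.

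**5. Simulation with no true effect.** All rates are assumed: 30-60% end the index drug by day 90, 10-20% are augmented by day 90 while on an antidepressant, 20-30% of those off all antidepressants restart after 30 days plus an exponential delay of mean 60 days, 0-75% of endings are switches, and items 1-5 occur independently at 5% by day 365.

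| Persistence cut | Events counted | Risk ratio, shorter vs longer |
|---|---|---|
| 180 days | days 91-180 | about 12-18 |
| 90 days | days 91-180 | 0.47-1.28 |
| 180 days | days 91-550 | 0.64-0.92 |

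**6. Does a landmark alone suffice?** In the middle set (50% ending, 10% augmented, 30% restarting), a day-90 landmark with items 6 and 7 kept still gave about 1.4 for days 91-180 and about 0.7-0.8 for days 91-550. Patients already off treatment at day 90 can meet item 7 soon afterwards, while those still on treatment must stop first but remain open to augmentation. With items 1-5 only, the landmark gave about 1.0. That value follows from simulating items 1-5 as unrelated to compliance. It shows that the built-in part is gone, not that real data would show no association.

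Dropping items 6 and 7 without a landmark is not enough either. If 25-50% of item 1-5 events on the index drug trigger a therapy change, the ratio for persistence below 180 against 180 days, with events in days 91-180, was 1.40-2.21.

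**7. What escapes the item 6 overlap.** Augmentation does not enter the MPR formula, and discontinuation is measured in the first 90 days and is listed separately from augmentation. A 30-day holiday starting after day 90 can leave a patient adherent: persistence is at least 90 and the 180-day MPR can be 150/180 = 0.83.

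**8. Follow-up available.** Index dates run to 30 June 2019 and data to 31 December 2020, which is 550 days. That leaves at least 550 − 90 = 460 days after day 90.

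**The case against.** Four points can be made for the plan.

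- **The study is exploratory.** SAP section 3 states no hypotheses, and the amendment is disclosed. That limits the severity. Protocol section 9.7 nevertheless sets a 0.05 significance level, and a descriptive association produced by definitions still misleads.
- **Augmentation or a restart can be genuine worsening.** This stands. It is a reason to keep the full composite in the report. It does not justify crossing the composite with a compliance measure that the same event ends.
- **Some time order is already there.** Item 4 can be read as using a 90-day MPR, persistence of at least 90 is settled at about day 90, discontinuation covers 90 days, recurrence is split at the end of the acute phase, and the section 7.2.2 population starts after day 90. On that reading the adherence flag is largely fixed before post-acute recurrence. But item 1 of section 5.1 gives MPR over 180 days, and persistence over 180 days is itself a named compliance measure.
- **The 180-day contrast is not the plan's own.** The only persistence cut in the SAP is 90. The range in "During the second 90 day period (91 ~ 180 days) starting from the index date" belongs to drug utilization pattern, a secondary variable, and recurrence has no stated end day. This stands.

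Because of the last point, a reader might infer from steps 1-3 that the definitions always make shorter persistence look worse, or that a ratio near 12-18 is the size of the bias. The documents support neither. Steps 4 and 5 show the reverse direction with a 90-day cut or longer follow-up.

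**Conclusion.** The overlap is in the SAP's wording, and nothing in the visible text of either document removes it. The two exact results, no item 6 or 7 recurrence in days 91-180 among patients persistent for 180 days and no adherent patient among those augmented with a listed drug before day 90, need no assumptions about rates.

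The direction and size of the distortion cannot be fixed from the documents. They depend on the compliance measure, the persistence cut and the recurrence window, and every ratio above rests on assumed rates. The point is limited to recurrence by compliance in section 7.2.2. It should be fixed, because that relationship belongs to a primary objective and cannot be interpreted as it is now defined.

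**What to change.** For recurrence by compliance in SAP section 7.2.2 only:

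1. Classify compliance from claims up to day 90 (90-day MPR and persistence to day 90). Count only recurrences after day 90, in patients event-free at that point, over a window whose last day is stated.
2. Report the relationship on items 1-5 alongside the seven-item composite broken down by component. Base any statement that compliance is associated with recurrence on the version without items 6 and 7, since the landmark alone does not remove their dependence on treatment status at day 90.
3. State how starting maintenance treatment is read. If it means still taking the index drug at day 90, the only patients with persistence below 90 are those who were augmented or given a second antidepressant, and the comparison shrinks to that.

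The cost is SAP wording and a re-run on data already held. There will be fewer events, and patients with an event before day 90 leave this one analysis. At least 460 days of possible follow-up remain after day 90, unless the patient dies or leaves the database.
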